International collaboration is established with the University of Alberta, Edmonton, Canada including the developer of the Edmonton Frail Scale, [name] (prof, geriatrician), Dept. of Geriatric Medicine.

User representatives: Our aim is to establish a group of 6 members (3 of each gender) > 65 years of age with experience from EBRT. Currently 4 members have been assigned from the local Breast Cancer Society and the local Prostate Society, respectively.

Reference group: Presently the group includes 11 cancer nurses and cancer co-ordinators representing 16 municipalities. We are aiming at including the remaining cancer coordinators (6-8) in the SI catchment area as well as representatives for the GPs.

Financial support

The study is fully financed by the Research Department at Innlandet Hospital Trust. No other financial partner is involved.

Time schedule

Start of enrolment is planned for February 2017 and will continue for 12 months or until the planned number of participants are included. The patients will be followed with study specific registrations for 16 weeks after the end of EBRT. Data on survival will be retrieved for up to 2 years after completion of EBRT. Furthermore, a PhD student and a project nurse will be contracted from the time of study start.

References

6. (IOM) IoM: Delivering High-Quality Cancer Care: Charting a New Course for a System in Crisis.

Although the study includes a two-year follow-up with respect to survival, OS was not a pre-defined outcome in this observational study. The exception was a plan to investigate the association between CT based muscle measure, inflammation and survival (protocol, page 18: “*Analysis of muscle mass and inflammation markers*”). One reason for this omission was that the association between GA defined frailty and OS was relatively well-documented in 2016, and thereby assumed to be of less interest than the outcomes QoL and PF.

The association between frailty/GA impairments and survival in older patients receiving EBRT is, however, currently still scarcely investigated, and therefore of interest.

Furthermore, the overarching aim of the present study was to “*generate knowledge that may provide a basis for developing a targeted and feasible intervention to prevent adverse events during and after curative and palliative EBRT in patients ≥ 65 years*”. Although not pre-defined as such in our study, death is the ultimate adverse event, and a gold standard endpoint in cancer studies. Hence, we found that investigating whether GA impairments are associated with mortality risk is both appropriate and pertinent, and well in line with the study purpose. Several of the impairments that may be identified by GA, are remediable. If any of these could have an impact on OS in patients with cancer receiving curative or palliative EBRT, developing and/or implementing interventions that specifically target these impairments would be highly important, i.e. in hope of improving an endpoint of major importance for the patients. Finally, when investigating the impact of GA impairments on global QoL, physical function and need for daily life assistance, it is crucial to know, whether the same impairments also affect OS.

Before any analysis for the first paper was conducted, a detailed analysis plan was prepared(**Appendix 1**). Subsequently, however, the definition of OS was corrected from “time from end of EBRT to death or last observation” to “time from inclusion to death or last

observation”, and we also decided to explore the association between number of GA impairments and OS.

2. OS will also be used as an outcome in the validation of the Edmonton Frail Scale, i.e. the planned second paper

The second secondary aim of our study is to “*Validate the Edmonton Frail Scale (EFS) as a screening instrument to identify frail patients and patients at risk of adverse events*” (see page 8).

The plan for the analyses was: “*The sensitivity and specificity of EFS in identifying frail patients will be tested against the full GA. EFS’ ability to predict adverse events on the defined outcomes will be assessed with uni- and multivariable regression analyses, controlled for relevant co-variates (e.g. type of cancer, stage of disease, and radiotherapy regimen*” (see page 17)

Partly based on the considerations stated under point 1, we have now decided to perform the validation by investigating the association between the instrument’s scores and OS in addition to association with GA findings. Another strong argument for this is that other well-known and widely used frailty screening instruments, e.g. the G8, have been widely tested against patients’ survival.¹⁻⁵ Thus, for comparison, which is important, we will do likewise.

Before embarking on these analyses, a detailed plan has also been prepared (**Appendix 2**).

3. We have decided not to use the term “frailty” when classifying the patients according to GA. Hence, we will not define the patients as frail or non-frail, but instead classify them according to their number of identified GA impairments.

Our primary hypothesis (page 8) has been revised accordingly, now reading: “*Our hypothesis is that increasing number of GA impairments is associated with increased risk of adverse events as defined, regardless of cancer type, stage, and radiotherapy procedure (localisation, dose, field size)*

This hypothesis and the primary aim of our study will be addressed in paper 3, for which a detailed plan for the analyses has also been prepared (**Appendix 3**)

This amendment also affects paper 2 as the sensitivity and specificity of Edmonton Frail Scale will be evaluated against number of geriatric deficits, not against a classification of frail vs. non-frail patients.

Explanation:

The concept of frailty has received increasing attention in oncology research since the start of the present study, and the understanding of the syndrome has also increased considerably. There is, however, still no consensus on how frailty should be defined based on GA. Former studies have used various numbers of GA impairments (from one to four) to identify patients as frail.⁶ Thus choosing a more or less arbitrary number to define frailty, we have realised, makes little sense. Furthermore, it is increasingly clear that frailty is developed as a

continuum from vulnerability to severe frailty.⁷ A classification as frail vs. non-frail therefore gives a poor description of the patients' vulnerability status, whereas this is reflected more correctly by number of geriatric deficits.

4. The fourth paper so far being planned is a description of the MoCA test results at baseline and during follow-up, and simultaneously an evaluation of the feasibility of this test for older patients with cancer. A detailed plan for the analyses has not yet been prepared.

This fourth paper will partly contribute to fulfil our primary aim 2 (evaluating the feasibility of GA performed in the municipalities) and secondary aim (describing the prevalence of geriatric problems after EBRT).

The reasons why we have chosen to look specifically on cognitive function and MOCA scores before evaluating the feasibility of the remaining GA registrations are:

- The MoCA test was assessment reported to cause most inconvenience for both patients and nurses. Patients with cancer, when consulting health care professionals, are not used to being cognitively evaluated, and some patients objected to this. For the same reason, some of the nurses also found it difficult to repeat the test after EBRT.
- Whether the MoCA test is relevant and appropriate for patients with cancer referred for new treatment, is poorly assessed. It is important to investigate if there might be a trend towards improvement from baseline through follow-up at home after EBRT, i.e. indicating that scores obtained before start of new treatment may not appropriately reflect the patients' cognitive function. According to some of the testing nurses, the scores seemed to be significantly affected by distress related to start of new treatment or other cancer-related problems.
- Overall, the trajectory of MoCA scores obtained from older patients with cancer receiving EBRT is scarcely described.

The overall feasibility of GA performed in the municipality, after EBRT, in this patient cohort will be evaluated in a subsequent paper.

5. We have decided not to assess the patients' muscle mass from available CT scans (as stated in the protocol page 17), hence these scans have not been retrieved.

The reason for this is our experience from a former study⁸ in another cohort of older patients with cancer. From that study, it was clear that as long as a baseline CT scan is not an obligatory part of the study design, or the procedures for such scans are not clearly defined, a large number of patients will not have scans taken within a reasonable time frame or at the appropriate body level including the overall body circumference. Hence, it is highly likely that the number of patients having non-available CT scans would be just as high in the present cohort as in our former study. Hence, the sample size for the planned analyses would most likely be too small. Furthermore, our former study, as well as another one recently

published,⁹ have found no association between muscle mass and frailty as defined by GA. Further investigations on the issue therefore seems futile.

References

5. van Walree IC, Scheepers E, van Huis-Tanja L, et al: A systematic review on the association of the G8 with geriatric assessment, prognosis and course of treatment in older patients with cancer. *J Geriatr Oncol*, 2019

Patient characteristics will be presented as means, standard deviations (SD), minimum and maximum values for continuous variables, and frequencies and percentages for categorical variables. Survival time, defined as time from end of radiotherapy (last fraction) to death or censoring (last observation) will be assessed by Kaplan-Meier plot and compared between groups using log-rank test. Bivariate and multiple Cox regression models will be used to investigate if frailty indicators specified above may predict the overall survival. The estimates will be adjusted for age, gender, type of cancer (lung cancer/breast cancer/prostate cancer/others), ECOG performance status and treatment intent (palliative versus curative intent).

To assess whether the predictors act differently in two treatment groups, the interactions between treatment intent variable and all other variables will be included. The Akaike's Information Criterion will be used to reduce the multiple model for excessive interactions. A significant interaction would imply that certain predictor predicts the overall survival differently in two treatment groups.

Appendix 2

Dated 14-12-20

Paper 2 from the study: Improving Quality of Life and Function for Older Cancer Patients Receiving Radiotherapy: an observational study

Paper investigating the relationship between Edmonton Frail Scale (EFS) scores and overall survival and the construct validity of EFS in relation to a geriatric assessment (GA)

Part 1: EFS in relation to survival in older patients receiving radiotherapy

The aims are to

- A) investigate if the Edmonton Frail Scale (continuous, scores 1-17) assessed at baseline is predictive of survival independent of age, gender and major cancer-related prognostic factors (treatment intent (curative vs. palliative), diagnostic groups and ECOG status)
- B) assess the survival of groups of patients classified according to proposed cut-off points for EFS scores (see below), and explore the data to find cut-off point(s) (potentially new) that best divide our cohort into groups with respect to survival

Proposed cut-off points and categories for the EFS scores

- 0-3 Fit
- 4-5 Vulnerable
- 6-7 Mild Frailty
- 8-9 Moderate Frailty
- 10+ Severe Frailty

Hypotheses

- A) EFS scores are independently predictive of survival in older patients referred for curative or palliative radiotherapy
- B) The survival of older patients with cancer referred for curative or palliative radiotherapy differ between the groups defined by formerly used/suggested cut-off points

Methods

- A) Cox proportional hazards regression model will be estimated
- B) Receiver Operating Characteristics curve analysis, Akaike's Information Criterion

Part II: Evaluate the concurrent validity of the EFS in a cohort of patients receiving radiotherapy

The aims are to

- A) describe the number and type of GA deficits within each of the formerly proposed categories of EFS (see above)
- B) assess the association between the formerly proposed EFS categories and number of GA deficits, and explore the data to find the cut-off point of EFS score that is most relevant to use in a screening procedure to ensure that the majority of patients in need of a full geriatric assessment are captured

Hypotheses

- A) the number of GA deficits increases according to the formerly proposed EFS categories (fit, vulnerable, mild frailty, moderate frailty and severe frailty) with patients with moderate/severe frailty having the highest number of GA deficits
- B) there is a significant association between EFS categories and number of GA deficits, and the proposed cut point EFS ≥ 6 for frailty is the appropriate cut-off point to ensure that a full GA is applied in patients where this is needed (based on number of GA deficits)

Methods

- A) Descriptive statistics
- B) ANOVA

Baseline data for EFS scores and the geriatric assessment will be used.

Appendix 3

Dated 18-05-21

Plan for analyses, paper no.3

Preliminary title:

Is the presence of geriatric impairments associated with quality of life and physical function after radiotherapy in older cancer patients? - A prospective observational study.

Main objectives:

In a cohort of older patients with cancer, referred for curative or palliative RT, we will:

1. assess the trend in quality of life (QoL) and physical function prior to and after RT for palliative and curative patients, and investigate if there is a significant difference in trend between the two groups
2. assess the trend in QoL and physical function prior to and after RT stratified on number of geriatric impairments present at baseline, and investigate if there is a significant difference in trend depending on the number of geriatric impairments

Predefined outcomes:

Primary: Global quality of life (QoL) and physical function as assessed by the European Organisation for Research and Treatment of Cancer Quality of Life Questionnaire (EORTC QLQ-C30) global QoL (gQoL) and physical functioning (PF) scale.

Secondary:

- Instrumental Activities of Daily Living (ADL)-function assessed by Nottingham Extended Index of Activities of Daily Living (NEADL) based on patients' self-report.
- Role function as assessed by the EORTC QLQ-C30 role function (RF) scale
- Fatigue and pain as assessed by the EORTC QLQ-C30 corresponding symptom scales (FA = fatigue)(PA = Pain)

Exploratory: Functioning and symptom scales/items of the EORTC QLQ-C30 that are not defined as primary or secondary outcomes will be assessed for explorative purposes

Hypotheses:

1. Patients referred for palliative RT have poorer scores for all primary and secondary outcomes prior to and after RT compared to patients referred for curative treatment
2. There is a significant difference in trend in outcomes for palliative and curative patients:
 - a. patients referred for palliative RT will experience an improvement in the primary outcomes global QoL and PF, and the secondary outcomes RF, NEADL and pain (PA) within 8 weeks after RT.
 - b. patients referred for curative RT will experience a deterioration in the primary outcomes global QoL and PF and the secondary outcomes RF, NEADL and

fatigue (FA) scores from baseline to 2 weeks after RT. Thereafter the scores will return to baseline values within 16 weeks.

3. There is a significant difference in trend in outcomes depending on number of geriatric impairments
 - a. scores for the primary outcomes global QoL and PF, and the secondary outcome RF decreases with increasing number of geriatric impairments
 - b. there is a significant association between number of geriatric impairments and the primary outcomes global QoL and PF as well as the secondary outcome RF scores

Timeline for the assessments: Patients answered EORTC QLQ-C30 and NEADL at five different time points: baseline, when completing RT (except palliative patients who received only a single fraction were per protocol test schedule not asked to answer EORTC QLQ-C30, and patients who received <10 fractions were not asked to answer NEADL), and 2, 8 and 16 weeks after RT. We will exclude the assessment of NEADL at the end of RT from our analyses because patients with short courses of RT did not fill in this questionnaire.

Statistical approach

Categorical baseline characteristics of curative and palliative patients will be described with frequencies and percentages, while continuous with means and standard deviations (SD) or median and min-max values.

Raw scores for all QLQ-C30 scales/items will be transformed into scales ranging from 0-100 in accordance with the official manual for this questionnaire. NEADL item scores will be summarized into a scale ranging from 0-66. Missing NEADL items scores will be imputed as follows:

The missing values are assumed to be missing at random (MAR), and will be imputed if at least half of the items of the scale had been answered. The imputation will be performed by generating an empirical distribution for each item based on non-missing values, and a random number drawn from it was used to replace the missing value.

To answer Study aim 1 and test our first hypothesis, the primary outcomes, global QoL and PF will be assessed by linear mixed model with fixed effects for (non-linear) time, treatment group (curative vs. palliative) and the interaction between the two. Random effects for patients will be included. The models will be adjusted for age, gender, performances status (ECOG PS) and cancer type. The secondary outcomes RF, NEADL and pain scores will be evaluated by similar models.

To answer Study aim 2 and test our second hypothesis, similar models to those describe for aim 1 will be performed for the primary outcomes global QoL and the secondary outcome RF. However, these models will use number of geriatric impairments as a stratification variable instead of treatment intent (palliative vs curative). The models will be adjusted for age, gender, cancer type, treatment intent (curative vs palliative) and ECOG PS.

Sensitivity analyses to estimate models for non-imputed variables for NEADL will be also be performed.

For explorative purposes linear mixed model with fixed effects for (non-linear) time, treatment group (curative vs. palliative) and the interaction between the two will be estimated to assess differences in trend between palliative and curative patients for emotional function (EF, insomnia, appetite loss). Similar models will also be estimated to assess possible differences in trend in pain, fatigue, insomnia, and appetite loss between groups defined according to number of geriatric impairments. For these models number of geriatric impairments will be used for stratification instead of treatment intent. No adjustments will be made in any of the explorative models.

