Our hypothesis is that patients, who are classified as frail, will have increased risk of deterioration in global QoL and physical functioning (PF), assessed by the corresponding EORTC QLQ-C30 scales ranging from 0-100. A difference of 10 points on these scales is considered a clinically significant difference.⁷⁶ Based on the reported prevalence of frailty in studies of other cohorts of older patients with cancer,^{18,43} one may assume that about 40% will be frail and 60% non-frail. To detect a difference of 10 points in global QoL and PF between the two groups at 8 weeks follow up, standard deviation (SD) = 30 (a conservative estimate), power 80% and significance level 5%, 119 patients will be needed in the frail group and 178 patients in the non-frail group, in total 297 patients. To document a difference of 11 points, 247 patients are needed. Based on these estimates, and taking into account that some drop out will occur, we find that including 325 patients will be satisfactory.

Strategy for the analyses

Adverse events are defined as described under Study aims, page 7-8. The patients will be classified as frail or non-frail based on GA at baseline. Primary and secondary outcomes will be compared between the non-frail and frail using bivariate regression analyses. Since the study cohort will be heterogeneous and several factors most likely will affect the outcomes, we will also estimate multivariate regression models, adjusted for these factors. The most important factors will be type of cancer, stage of disease, gender and radiotherapy regimen. Time trend models will be estimated in order to assess the development in the primary outcomes for non-frail/frail patients during the follow up period. We will also estimate bi- and multivariate regression models to assess the impact of each individual factor in GA (i.e. comorbidity, physical function, nutritional status) on the defined outcomes. Furthermore, we will use descriptive statistics to compare sociodemographic and medical data and GA findings between patients experiencing and not experiencing adverse events.

The sensitivity and specificity of EFS in identifying frail patients will be tested against the full GA. EFS ability to predict adverse events on the defined outcomes will be assessed with uni- and multivariate regression analysis, controlled for relevant co-variates (e.g. type of cancer, stage of disease, and radiotherapy regimen).

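### Appendix 2 Part II B lists only ANOVA for choosing an Edmonton Frail Scale screening cut-off; the sensitivity and specificity promised in Amendment 4 are not worked into it

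*Combined protocol and SAP*

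**What the plan says.** Appendix 2, Part II, Aim B has two halves. The first is the association between the proposed EFS categories and the number of GA deficits. The second is to "explore the data to find the cut-off point of EFS score that is most relevant to use in a screening procedure", with the stated purpose "to ensure that the majority of patients in need of a full geriatric assessment are captured". Hypothesis B likewise expects an association and adds that "the proposed cut point EFS ≥ 6 for frailty is the appropriate cut-off point". The Methods entry for B is ANOVA and nothing else.

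The neighbouring entries are assigned by part and letter. Part II A is to "describe the number and type of GA deficits within each of the formerly proposed categories of EFS", by descriptive statistics. "Receiver Operating Characteristics curve analysis" appears under Part 1 B, whose aim and hypothesis concern survival.

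Elsewhere the document commits to accuracy measures. The protocol's analysis strategy says: "The sensitivity and specificity of EFS in identifying frail patients will be tested against the full GA". Amendment 4, point 3, drops the frail/non-frail classification and says for paper 2 that "the sensitivity and specificity of Edmonton Frail Scale will be evaluated against number of geriatric deficits". Amendment 4, point 2, presents Appendix 2 as the detailed plan for these analyses.

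**The concern.** Whether a cut-off captures most of the patients who need a full GA is a question of sensitivity. It requires a definition of who is in need and a rule for how many must be captured. ANOVA compares mean deficit counts between groups and addresses neither. Amendment 4 names the right quantities, but the detailed plan gives no reference deficit count, no number for the majority to be captured and no rule for choosing or accepting a cut-off.

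The practical risk is that a significant ANOVA, which is very likely here, is taken as confirming EFS 6 or more although it says nothing about how many patients with deficits score below 6. Validation of the EFS is a declared secondary aim, so its screening conclusion is what is at stake. The EFS cut-off does not enter the quality-of-life and physical-function analyses of paper 3.

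**Working it through.** The plan states no figure for this analysis, so there is none to reproduce. The check is a comparison of tasks with methods, followed by an illustration.

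**Step 1. Tasks against methods (Appendix 2, Part II B)**

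| Task | Method listed | Does it answer the task? |
|---|---|---|
| Association of EFS categories with deficit count | ANOVA | Yes |
| Choose a screening cut-off | ANOVA | No |
| Judge EFS 6 or more | ANOVA | No |

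**Step 2. Why ANOVA cannot do the last two.** With five EFS categories (0-3, 4-5, 6-7, 8-9, 10 or more) and N = 301 (Appendix 1),

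F = [Σ n_k(ȳ_k − ȳ)² / (5 − 1)] / [ΣΣ(y_ik − ȳ_k)² / (301 − 5)].

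No term contains a cut-off c or a reference count d. The quantity needed is sensitivity = P(EFS ≥ c | deficits ≥ d), which contains both.

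**Step 3. Illustration on assumed inputs.** Only N = 301 and the EFS categories come from the documents. Assumed:
- EFS: gamma, mean 4, 4.5, 5 or 5.5, SD 2.8, rounded to 0-17. This puts 24% to 43% at 6 or more.
- Deficits: negative binomial, mean 2.7, dispersion 3, capped at 9. This gives 85%, 65%, 45% and 30% with at least 1, 2, 3 and 4 deficits.
- Gaussian-copula correlation of 0.5, 0.6, 0.7 or 0.8. In total there are 4 × 4 = 16 settings.

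ANOVA: 300 datasets per setting, 16 × 300 = 4,800, all with p < 0.05 (largest p 1.3e-05). At a correlation of 0.3, 97% to 98% were significant.

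Sensitivity of EFS 6 or more in the same settings:

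| In need means at least | Range over 16 settings | EFS mean 5, r = 0.6 |
|---|---|---|
| 1 deficit | 27-50% | 41% |
| 2 deficits | 32-63% | 49% |
| 3 deficits | 38-76% | 57% |
| 4 deficits | 44-86% | 65% |

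Part of this is simple arithmetic: sensitivity cannot exceed P(EFS ≥ 6) / P(deficits ≥ d). For at least 1 deficit that cap is 24/85 = 28% to 43/85 = 51%, however strong the correlation.

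Taking the majority as more than 50%, the criterion is met in 31 of 16 × 4 = 64 combinations. Within a setting, the four deficit counts disagree in 13 of 16; all four fail in 2 and all four pass in 1. The verdict on EFS 6 or more therefore turns on a reference count that the plan does not set.

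**Step 4. The number behind the majority also matters.** At EFS mean 5, r = 0.6 and at least 3 deficits, the highest qualifying cut-off is 6 for sensitivity over 50%, 4 for over 80% and 3 for over 90%.

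**Step 5. Could sensitivity be estimated usefully?** Wilson 95% interval: [p + z²/2n ± z√(p(1 − p)/n + z²/4n²)] / (1 + z²/n), z = 1.96. Numbers in need under the assumed prevalences: 301 × 0.65 = 196 (at least 2 deficits) and 301 × 0.30 = 90 (at least 4).
- For 72/90: (0.8 + 0.0213 ± 0.0854)/1.0427 = 71% to 87%.
- For 157/196: 74% to 85%.
- At 50%: 43% to 57% with 98/196, and 40% to 60% with 45/90.

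Precision is adequate with baseline data already held.

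**The case against.** The strongest defence is that the document, read as a whole, does plan an accuracy analysis. Amendment 4 states it for paper 2, and it refers to Appendix 3 (dated 18-05-21) as already prepared, so its text is later than Appendix 2 (14-12-20). A reader might infer that the plan contains no accuracy analysis of the EFS. That is too strong: the intention is current, and what is missing is its working-out in Appendix 2.

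Second, Part II A could supply most of the data. Since 6 is a boundary of the EFS categories, a table of deficit counts by category would give sensitivity and specificity of EFS 6 or more at any deficit count by arithmetic. This stands, provided that full counts are tabulated. It still leaves the reference count and the decision rule open.

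Third, the cut-off search is described as exploring the data, and Amendment 4 deliberately declines a single frailty threshold because "Former studies have used various numbers of GA impairments (from one to four) to identify patients as frail". A fixed target is therefore optional for the search itself. Hypothesis B, however, asserts that a particular cut-off is appropriate, and that cannot be judged without a reference and a criterion.

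Fourth, the ROC analysis in Part 1 might be meant to serve Part II too. The text does not say so: methods are assigned by part and letter, and that entry belongs to survival.

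Finally, the simulation rests on chosen inputs. The EFS SD and the deficit distribution were not varied, and 31 of 64 counts cells in a chosen grid. That ANOVA does not evaluate a cut-off holds by logic, without the simulation.

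**Conclusion.** The point holds as a gap between Amendment 4 and the detailed plan. Part II B names a method for the association only; the accuracy evaluation that Amendment 4 commits to has no measure, reference deficit count or decision rule in Appendix 2. A significant ANOVA is near certain under any moderate correlation (all 4,800 datasets at 0.5 to 0.8, and 97% to 98% at 0.3, under the assumed distributions) and carries no information on whether EFS 6 or more meets the plan's own criterion.

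A reader might also infer that EFS 6 or more is a poor cut-off in this cohort. Nothing here supports that: the EFS and deficit distributions are assumed, and the criterion was met in about half of the combinations.

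This should be put right before the paper 2 analysis. It bears on the screening conclusion of a secondary aim. Which GA measures are counted as deficits, and at what impairment cut-offs, also affects papers 1 and 3 and belongs in a separate point.

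**What to change.** In Appendix 2, Methods II B:

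1. Keep ANOVA, or a trend test, and state that it addresses the association only.
2. Add sensitivity, specificity, PPV and NPV of EFS 6 or more with 95% confidence intervals, and ROC/AUC for the EFS score, against number of GA deficits.
3. Before analysis, name one deficit count as the primary reference for needing a full GA, and the numeric sensitivity that the majority stands for. Judge EFS 6 or more on that reference. Report the other counts in the range from 1 to 4 or more, which Amendment 4 cites from former studies, as sensitivity analyses.
4. Label any alternative cut-off exploratory and correct its accuracy for optimism, for example by bootstrap.

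A single primary reference is needed because judging the cut-off at all four counts with equal standing would usually leave Hypothesis B undecided. It serves this screening analysis only and labels no patient as frail, so it can stand beside Amendment 4's reasons for dropping that term.

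The cost is SAP wording and routine analysis of existing baseline data. The downsides are that a primary count must be agreed, and that EFS 6 or more may look less favourable than ANOVA alone would suggest.
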